1.6. Compliance

This study will be conducted in compliance with this protocol, Good Clinical Practice (GCP), and all applicable regulatory requirements.

2. OBJECTIVES

The primary objectives of this study are as follows:

- To evaluate the efficacy of switching to TAF 25 mg QD versus continued TDF 300 mg QD in virologically suppressed subjects with chronic HBV as determined by the proportion of subjects with HBV DNA ≥ 20 IU/mL (as defined by the modified US FDA-defined snapshot algorithm) at Week 48
- To compare the safety and tolerability of switching to TAF 25 mg QD versus continuing TDF 300 mg QD in virologically suppressed subjects with chronic HBV at Week 48

The key secondary objectives of this study are as follows:

- To compare the safety of switching to TAF 25 mg QD versus continued TDF 300 mg QD as determined by the percent change from baseline in hip and spine BMD at Week 48
- To compare the safety of switching to TAF 25 mg QD versus continued TDF 300 mg QD as determined by the change from baseline in estimated creatinine clearance by Cockcroft-Gault method (eGFR_{CG}) at Week 48

Other secondary objectives of this study are as follows:

- To evaluate the proportion of subjects with HBV DNA < 20 IU/mL and target detected/not detected (i.e. < LLOD) at Week 48 in subjects switched to TAF 25 mg QD versus continued TDF 300 mg QD
- To compare the safety of switching to TAF 25 mg QD versus continued TDF 300 mg QD for 48 weeks followed by open-label TAF for 48 weeks as determined by the percent change from baseline in hip and spine bone mineral density (BMD) at Week 96
- To compare the safety of switching to TAF 25 mg QD versus continued TDF 300 mg QD as determined by the change from baseline in estimated creatinine clearance by Cockcroft-Gault method (eGFR_{CG}) at Week 96
- To compare the serological response (loss of HBsAg and seroconversion to anti-HBs, and loss of HBeAg and seroconversion to anti-HBe in HBeAg-positive subjects) of switching to TAF 25 mg QD versus continued TDF 300 mg QD at Week 48
- To compare biochemical response (normal ALT and normalized ALT) of switching to TAF 25 mg QD versus continued TDF 300 mg QD at Week 48

- To compare the change in fibrosis as assessed by FibroTest[®] after switching to TAF 25 mg QD versus continued TDF 300 mg QD at Weeks 48
- To evaluate the comparative open-label efficacy and safety of switching to TAF 25 mg QD from Week 48 through Week 96 in subjects initially randomized to TAF 25 mg QD and in subjects sequentially treated with continued TDF 300 mg QD for 48 weeks and then switched to open-label TAF 25 mg QD

The exploratory objectives of this study are as follows:

3. STUDY DESIGN

3.1. Study Treatment Plan and Regimen

This is a randomized, double-blind, multicenter, active-controlled study to evaluate the safety and efficacy of TAF 25 mg QD in virologically suppressed subjects who switch from TDF to TAF compared to continued TDF treatment.

Approximately 460 subjects (with approximately 50% of subjects being \geq 50 years old) will be randomized in a 1:1 ratio (A:B) to receive either TAF 25 mg QD and matched placebo of TDF 300 mg QD or Gilead-provided TDF 300 mg QD and matched placebo of TAF 25 mg QD.

At randomization, subjects will be stratified by screening HBeAg status (HBeAg-negative vs. HBeAg-positive) and age (> 50 or < 50 years).

- Treatment Arm A: approximately 230 subjects administered TAF 25 mg QD and matched placebo of Tenofovir DF (TDF) 300 mg QD
- Treatment Arm B: approximately 230 subjects administered Gilead-provided TDF 300 mg QD and matched placebo of TAF 25 mg QD

The duration of double blind treatment is 48 weeks. All subjects who complete 48 weeks of treatment are eligible for participation in the open label TAF 25 mg extension period for an additional 48 weeks (through Week 96). During the double-blind period, subjects with a confirmed creatinine clearance by Cockcroft Gault Method (eGFR_{CG}) < 50 ml/min, and > 20% decline in eGFR by CKD-EPI (cystatin C) compared to baseline during the study, will be required to undergo dose modification to every other day dosing of study drug. Subjects with confirmed creatinine clearance < 30 mL/min during the double blind phase of the study will have the study drug permanently discontinued. Subjects with confirmed eGFR_{CG} < 50 mL/min will not undergo dose modification to every other day during the open-label TAF 25 mg extension period, nor will treatment be permanently discontinued for confirmed eGFR_{CG} < 30 mL/min during the open-label extension period.

Subjects who permanently discontinue study drug (either prematurely or at the end of study [Week 96]) for reasons other than HBsAg loss with confirmed seroconversion to anti-HBs will be followed every 4 weeks for 24 weeks off treatment or until initiation of appropriate alternative, HBV therapy, whichever occurs first. Use of appropriate, alternative HBV therapy is strongly encouraged.

Subjects with HBsAg loss, and confirmed seroconversion to anti-HBs should discontinue study drug within 3-6 months following confirmation of seroconversion to anti-HBs. Subjects with HBsAg loss with confirmed seroconversion prior to Week 48 are not permitted to discontinue study drug prior to the Week 48 visit. Subjects with HBsAg loss with confirmed seroconversion will be followed off treatment every 4 weeks for 12 weeks and then per the study visit schedule (Appendix 2) through Week 96/ED. Discontinuation of study drug for subjects experiencing HBsAg loss with confirmed seroconversion, who have known bridging fibrosis or cirrhosis, should be considered on a case by case basis.

The primary analysis will occur at Week 48 with the primary efficacy endpoint being the proportion of subjects with HBV DNA \geq 20 IU/mL, as determined by the modified US FDA-defined snapshot algorithm.

An external, independent, multidisciplinary DMC will review the progress and safety of this study. The committee will convene after the last subject enrolled completes Week 24 of the study. However, Gilead will defer to the DMC for any decision to convene earlier or more frequently. At each meeting, the DMC will review routine safety and DXA data and will make recommendations regarding modification of the study treatment.

Subjects with a history of or current diagnosis of compensated cirrhosis (i.e. those with cirrhosis without laboratory or clinical evidence of decompensated liver disease) are eligible for enrollment. Acceptable diagnostic criteria for cirrhosis include a Metavir or Knodell fibrosis score ≥ 4 or Ishak fibrosis score ≥ 5 by liver biopsy, a Fibrotest score ≥ 0.75 , or previous Fibroscan result > 12kPa (in countries where locally approved). Available information regarding the presence or absence of cirrhosis by these criteria will be captured in the electronic case report forms at Baseline, and any other time during the trial should an investigator opt to undertake additional studies. Available information regarding hepatic status will be assessed by Child-Pugh score and will be captured in the electronic case report forms at Baseline, Weeks 48 and 96. The change in fibrosis as assessed by Fibrotest[®] will be performed in all subjects participating in the trial at Baseline, and Weeks 48, and 96/ED.

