8.4. Multiplicity Adjustments

To control type I error for the assessment of the primary efficacy endpoint and key secondary safety endpoints, the hypothesis testing will be performed in a sequential order. The primary hypothesis of non-inferiority of TAF 25 mg QD vs. TDF 300 mg QD with respect to the proportion of subjects with HBV DNA \geq 20 IU/mL (as defined by the modified US FDA-defined snapshot algorithm) at Week 48 will be tested first. The non-inferiority test will be performed using a two-sided, 0.05 alpha level. If non-inferiority is established, then multiplicity adjustments will be performed for the following endpoints using a fallback procedure {Wiens 2005} in the sequential order given below with a pre-specified two-sided alpha level:

- a) Percentage change from baseline in Hip BMD at Week 48 (alpha = 0.02)
- b) Percentage change from baseline in Spine BMD at Week 48 (alpha = 0.01)
- c) Change from baseline in Creatinine clearance (eGFR_{CG}) at Week 48 (alpha = 0.02)
- d) Superiority test for proportion of subjects with HBV DNA \geq 20 IU/mL at Week 48 (alpha = 0.00)

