8.7.1. Key Secondary Safety Analyses

The percent change from baseline in hip and spine BMD at Week 48 will be analyzed using an ANOVA model. The model will include treatment group as fixed effect. The detailswill be provided in the Statistical Analysis Plan (SAP).

The change from baseline in in eGFR $_{CG}$ at Week 48 will be analyzed using a 2-sided Wilcoxon rank sum test to compare the 2 treatment groups. The details will be provided in the SAP.

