8.9. Sample Size

With respect to the primary efficacy endpoint of proportion of suppressed subjects with HBV DNA \geq 20 IU/mL (current assay LLOQ), as determined by the modified US FDA-defined snapshot algorithm, at Week 48, when the sample sizes are 230 (TAF 25 mg arm) and 230 (TDF 300 mg arm), a two-group, large-sample normal approximation test of proportions with a one-sided 0.025 significance level will have 80% power to establish non-inferiority of TAF to TDF. It is assumed that both treatment arms will have subjects who have HBV DNA \geq 20 IU/mL (as defined by the modified US FDA-defined snapshot algorithm) at a rate of 2.4% at Week 48 (based on the rates of suppressed subjects having HBV DNA \geq 29 IU/mL [the LLOQ of assay during those studies] after 48 weeks of treatment from the combined data of studies GS-US-174-0102 and GS-US-174-0103 with the ratio of HBeAg- to HBeAg+ subjects assumed to be 2:1), with a non-inferiority margin of 4%.

The proposed sample size (n = 230 for the TAF 25 mg arm, n = 230 for the TDF 300 mg arm) also provides > 99% power to detect a 1.81% difference in the percentage change from baseline in hip BMD at Week 48 (assuming a 1.47% [SD 2.71%] change from baseline in TAF 25 mg arm and -0.34% [SD 2.83%] change from baseline in the TDF 300 mg arm, with a two-sided $\alpha = 0.05$); a > 99% power to detect a 2.00% difference in the percentage change from baseline in spine BMD at Week 48 (assuming a 1.56% [SD 3.84%] change from baseline in the TAF 25 mg arm and -0.44% [SD 4.14%] change in the TDF 300 mg arm, with a two-sided $\alpha = 0.05$); a 97% power to detect a 4.9 mL/min difference in the change from baseline in eGFR_{CG} at Week 48 (assuming a 1.3 mL/min [SD 13.2] change from baseline in the TAF 25 mg arm and -3.6 mL/min [SD 13.0] change from baseline in the TDF 300 mg arm, with a two-sided $\alpha = 0.05$). These assumptions were derived from an HIV switch study (GS-US-292-0109) due to the unavailability of switch data from TAF HBV studies.

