7.4.3. Estimated Glomerular Filtration Rate

Estimated glomerular filtration rate will be summarized for subjects in the Safety Analysis Set from baseline to Week 96.

The following formulae will be used to calculate eGFR:

• CG based:

```
eGFRcg (mL/min) [(140 age (yrs)) \times weight (kg) \times (0.85 if female)] / (SCr (mg/dL) \times 72), where weight is actual total body mass in kilograms, and SCr is serum creatinine.
```

• CKD-EPI Creatinine based:

```
eGFRCKD EPI, creatinine (mL/min/1.73 m^2) 141 \times \min(SCr/\kappa, 1)^{\alpha} \times \max(SCr/\kappa, 1)^{1.209} \times 0.993^{age} \times 1.018 (if female) \times 1.159 (if black),
```

where κ is 0.7 for females and 0.9 for males, α is 0.329 for females and 0.411 for males, min indicates the minimum of SCr/ κ or 1, and max indicates the maximum of SCr/ κ or 1 {Levey 2009}.

• CKD-EPI Cystatin C based:

```
eGFRCKD EPI, cysC (mL/min/1.73 m^2) 133 \times min(SCys/0.8, 1)^{0.499} \times max(SCys/0.8, 1)^{1.328} \times 0.996^{age} [\times 0.932 \text{ if female}],
```

where SCys is serum cystatin C.

P-values for the baseline, the change from baseline in eGFR $_{CG}$ and eGFR $_{CKD}$ $_{EPI,\ creatinine}$ will be estimated from the 2-sided Wilcoxon rank sum test to compare the 2 treatment groups. For eGFR $_{CKD}$ $_{EPI,\ cysC}$, only the baseline value will be summarized as the postbaseline tests were only performed as reflex tests.

The number and proportion of subjects with decrease from baseline of $\geq 25\%$ and $\geq 50\%$ in eGFRcg and eGFR ckd EPI, creatinine will be summarized by treatment groups for subjects in the Safety Analysis Set from baseline to Week 96. Statistical comparisons of the subject incidence rates between the 2 treatment groups during the entire study period will be performed using Fisher's exact test.

The number and proportion of subjects in each stage of chronic kidney disease (CKD) will be summarized by baseline stages of CKD at Weeks 12, 24, 36, 48, 60, 72, and 96 for the entire study treatment period based on subjects in the Safety Analysis Set. The distribution of the stages of CKD at these visits will be compared between the 2 treatment groups adjusting for entire study treatment period using rank ANCOVA {LaVange 2008}.

The stages of CKD are defined as follows:

- Stage 1: eGFRcg≥ 90 mL/min
- Stage 2: eGFRcg \geq 60 and \leq 90 mL/min
- Stage 3: eGFRcg \geq 30 and \leq 60 mL/min
- Stage 4: eGFRcg < 30 mL/min

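### The eGFR_CG comparison is a valid but unadjusted Wilcoxon test, and the supplied plans give no between-arm difference with a confidence interval; an adjusted estimate would be a free, optional improvement

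*Protocol*

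**What the plan says.** Protocol 3.1 sets the randomisation factors: "At randomization, subjects will be stratified by screening HBeAg status (HBeAg-negative vs. HBeAg-positive) and age" (cut at 50 years). The renal key secondary objective in Protocol 2 is to compare the arms "as determined by the change from baseline in estimated creatinine clearance by Cockcroft-Gault method". Protocol 8.4 puts it third in the fallback sequence: "c) Change from baseline in Creatinine clearance (eGFR_{CG}) at Week 48 (alpha = 0.02", after hip BMD (0.02) and spine BMD (0.01).

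Protocol 8.7.1 says the change "at Week 48 will be analyzed using a 2-sided Wilcoxon rank sum test to compare the 2 treatment groups" and defers details to the SAP. The supplied SAP covers the final analysis. In its section 7.4.3, p-values for baseline and change in eGFR_CG "will be estimated from the 2-sided Wilcoxon rank sum test to compare the 2 treatment groups".

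No stratum or covariate is named for this test in either document. What is planned beside it:
- n, mean, SD, median and quartiles by arm (Protocol 8.6.2);
- plots of median change (SAP 7.4.3);
- Fisher tests of declines of at least 25% and 50% (SAP 7.4.3);
- CKD stage tabulated by baseline stage and compared by rank ANCOVA (SAP 7.4.3).

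**The concern.** Two things are left unused.

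**Estimate.** The endpoint is powered on a difference in mL/min, but nothing in the supplied documents estimates that difference with its uncertainty. The same SAP (6.2.2) plans differences with 95% CIs, from models containing HBeAg status and age, for log10 HBsAg, ALT and FibroTest, none of which is in the fallback sequence. The Protocol's own summary of the earlier Phase 3 studies (1.2.3) shows the practical result. Hip BMD has a least-squares mean difference with a CI (1.697; 1.420 to 1.974), while eGFR_CG has two medians (-1.2 and -5.4 mL/min) and a p-value.

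**Adjustment.** Baseline eGFR_CG is collected in everyone and will usually predict the change through regression to the mean. The randomisation strata are used for the primary endpoint (Protocol 8.6.1) and for several secondary ones, but not here. Rank ANCOVA is already in the SAP for BMD status (7.3.1), CKD stage (7.4.3), UPCR and UACR categories (7.4.6) and Child-Pugh class (7.5), so no new method is needed.

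At stake are some precision and an interpretable effect size for one of three alpha-controlled safety claims.

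**Working it through.** **Inputs (Protocol 8.9).** 230 per arm. For TAF: "assuming a 1.3 mL/min [SD 13.2] change from baseline in the TAF 25 mg arm". For TDF, the Protocol takes a mean decline of 3.6 mL/min with SD 13.0. The difference is 1.3 - (-3.6) = 4.9 mL/min. The stated result is "a 97% power to detect a 4.9 mL/min difference in the change from baseline in eGFR_{CG} at Week 48", at two-sided 0.05.

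**1. Reproduce the stated power.**
- Pooled SD = sqrt((13.2² + 13.0²)/2) = 13.10.
- SE = 13.10 × sqrt(2/230) = 1.22 mL/min.
- Two-sample normal test: 4.9/1.2216 - 1.960 = 2.05, power 98.0%.
- Wilcoxon under normality (relative efficiency 3/π, so SE × sqrt(π/3) = 1.250): 4.9/1.250 - 1.960 = 1.96, power 97.5%. Noether's formula gives 97.2% and a simulation of 20,000 trials 97.5%.

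The plan's 97% is reproduced.

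**2. Which alpha applies.** Under the fallback procedure eGFR_CG is tested at 0.02 at least, and at 0.02 + 0.01 + 0.02 = 0.05 if hip and spine BMD are both significant. On the plan's BMD inputs:
- Hip at 0.02: SD 2.77, SE 0.258, 1.81/0.258 = 7.01; 7.01 - 2.33 = 4.68, power above 99.9%.
- Spine at the accumulated 0.03: SD 3.99, SE 0.372, 2.00/0.372 = 5.37; 5.37 - 2.17 = 3.20, power 99.9%.

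If those inputs are right, 0.05 is the level eGFR_CG will almost certainly get. At the 0.02 floor the planned Wilcoxon test has 94.5% power (3.92 - 2.33 = 1.59).

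**3. Gain from using baseline.** The correlation r between baseline and Week 48 eGFR_CG is not in the documents; 0.7 to 0.9 is assumed. With equal variances σ² at both times, the change has variance 2σ²(1 - r) and the baseline-adjusted residual has σ²(1 - r²). The ratio is (1 + r)/2.

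| r | Variance ratio | SE (mL/min) | 95% CI half-width | Power at 0.05 | Power at 0.02 |
|---|---|---|---|---|---|
| no adjustment | 1.00 | 1.22 | 2.39 | 97.5% | 94.5% |
| 0.9 | 0.95 | 1.19 | 2.33 | 98.0% | 95.5% |
| 0.8 | 0.90 | 1.16 | 2.27 | 98.5% | 96.5% |
| 0.7 | 0.85 | 1.13 | 2.21 | 98.9% | 97.3% |

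The power columns are for rank-based tests, taking 3/π efficiency in every row. SE and half-width are for the mean difference. The gain is 0.5 to 1.4 points at 0.05 and about 1 to 3 points at 0.02.

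**4. What a reported estimate would look like.** At the planned effect the unadjusted interval is 4.9 ± 2.39, or about 2.5 to 7.3 mL/min. With r = 0.7 it would be 4.9 ± 2.21, or about 2.7 to 7.1.

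**The case against.** The strongest reply is that the plan is sound as written. An unstratified test after stratified randomisation is normally conservative, randomisation already balances the two strata, and the endpoint has ample power. No document links HBeAg status to eGFR change, and age in the Cockcroft-Gault formula mainly sets the level, since everyone ages by the same 48 weeks. All of this stands. It is why the gain is small, and it makes baseline eGFR_CG, rather than the strata, the covariate most likely to help.

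A second reply concerns timing and missing documents. SAP 2.2 reports the Week 48 analysis as done, and SAP 6.1.1 refers to a separate Week 48 SAP that is not among the documents. Replacing the alpha-controlled test now would be post hoc, and the missing interval is shown only for the Protocol and the final-analysis SAP. The Week 96 comparison lies outside the fallback sequence. This also stands and limits the fix.

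A reader might infer three stronger things that the documents do not support:
- That baseline is ignored. The variable tested is change from baseline; baseline is only not a covariate.
- That the size of the effect goes unreported. By-arm means, SDs and medians are planned, so a reader could form an unadjusted mean difference and rough interval. What is absent is a planned estimate with its CI.
- That type I error is at risk or power inadequate. Neither follows.

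**Conclusion.** The point holds as a free improvement, optional rather than the correction of an error. The supplied documents plan an unadjusted Wilcoxon test for eGFR_CG change and no between-arm difference with a CI. The missing interval matters more than the lost precision, which amounts to a standard error of 1.22 rather than 1.13 to 1.19 mL/min, and one to three points of power at most.

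Those sizes rest on the plan's SDs, on all 230 subjects per arm contributing, on normality, and on the assumed correlation of 0.7 to 0.9; a correlation nearer 1 would shrink the gain further. The Week 48 SAP could settle whether an interval was already planned there.

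**What to change.** In Protocol 8.7.1 and SAP 7.4.3:
- Report the between-arm difference in eGFR_CG change with a 95% CI, adjusted for baseline eGFR_CG and the randomisation strata. A Hodges-Lehmann shift with its CI is an acceptable alternative.
- Use rank ANCOVA with baseline eGFR_CG as covariate, stratified by HBeAg status and age group, as the test, and keep the plain Wilcoxon test as a sensitivity analysis.
- For Week 48, where the test has already been run, leave the prespecified Wilcoxon test as the alpha-controlled result and add the adjusted estimate with its CI, labelled supplementary.

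The cost is an edit to the Protocol and SAP text and a few lines of code. No new data are needed.

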3.2. Biomarker Testing

[figure not shown]
3.2.1. Biomarker Samples to Address the Study Objectives

The following biological specimens will be collected in this study and will be used to evaluate the association of exploratory biomarkers with study drug response, including efficacy and/or adverse events and to increase knowledge and understanding of the biology of chronic hepatitis B and related diseases. The specific analyses will include, but will not be limited to, the biomarkers listed below. Because biomarker science is a rapidly evolving area of investigation, and adverse events in particular are difficult to predict, it is not possible to specify prospectively all tests that will be done on the specimens provided. The testing outlined below is based upon the current state of scientific knowledge. It may be modified during or after the end of the study to remove tests no longer indicated and/or to add new tests based upon the growing state of art knowledge.

- Fasting Urine Biomarkers including, but not limited to, retinol binding protein (RBP) and beta-2 microglobulin
- Fasting Serum Bone Biomarkers including, but not limited to, C-type collagen sequence (CTX) and procollagen type 1 N-terminal propertide (P1NP)

These specimens will be collected from all subjects in a fasted state at Baseline and Weeks 4, 12, 24, 48, 72, and 96/ED. **PPD**

3.2.2. Biomarker Samples for Optional Future Research

3.3. End of Study

End of Study is defined as when the last subject has completed 96 weeks of treatment, or when the last subject has completed 96 weeks of treatment and up to 24 weeks of treatment free follow-up if appropriate, alternative anti-HBV treatment is not initiated after completing 96 weeks of study treatment.

3.4. Post Study Care

Once a subject has completed their study participation, the long-term care of the participant will return to the responsibility of their primary treating physicians.

4. SUBJECT POPULATION

4.1. Number of Subjects and Subject Selection

Approximately 460 subjects (with approximately 50% of subjects being \geq 50 years old) will be randomized in a 1:1 ratio (A:B) to receive either TAF 25 mg QD and matched placebo of TDF 300 mg QD or Gilead-provided TDF 300 mg QD and matched placebo of TAF 25 mg QD.

4.2. Inclusion Criteria

Subjects must meet all of the following inclusion criteria to be eligible to participate in the study:

- 1) Must have the ability to understand and sign a written informed consent form; consent must be obtained prior to initiation of study procedures
- 2) Adult male and non-pregnant, non-lactating female subjects, ≥18 years of age based on the date of the screening visit. A negative serum pregnancy test at Screening is required for female subjects of childbearing potential (as defined in Appendix 5).
- 3) Documented evidence of chronic HBV infection previously (e.g., documented HBsAg positive for more than 6 months)
- 4) Maintained on TDF 300 mg QD for at least 48 weeks, and as monotherapy for CHB for at least 24 weeks prior to screening and with viral suppression (HBV DNA < LLOQ by local laboratory assessment) for a minimum of 12 weeks prior to Screening, and including a Screening HBV DNA value of < 20 IU/mL (by central laboratory)
- 5) Estimated creatinine clearance ≥ 50 ml/min (using the Cockcroft-Gault method) based on serum creatinine and actual body weight as measured at the Screening evaluation, as follows:

(Note: multiply estimated rate by 0.85 for women)

- 6) Normal ECG (or if abnormal, determined by the Investigator not to be clinically significant)
- 7) Must be willing and able to comply with all study requirements

